#### *Serologically-confirmed SARS-CoV-2 Infection*

Defined as a positive result in serum for the presence of antibodies specific to the nucleoprotein of SARS-CoV-2 detected by electrochemiluminescence immunoassay (ECLIA).

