## 9.3 Populations for Analyses

The following populations are defined:

Population	Description
Enrolled	All participants with a dose-level group that has been allocated by IRT
Safety Analysis Set (SafAS)	Subset of enrolled participants who have received at least 1 injection of study intervention. Participants will have their safety analyzed according to the study intervention they actually received.

Population	Description
	Safety data recorded for a vaccine received out of the protocol design will be excluded from the analysis (and listed separately).
Full Analysis Set (FAS)	Subset of enrolled participants who received at least 1 injection of the study intervention. Participants will be analyzed according to the intervention to which they were enrolled.
Per-Protocol Analysis Set (PPAS)	
Subset of the FAS. Participants presenting with at least 1 of the following relevant conditions will be excluded from the PPAS:
 
 
• Participant did not meet all protocol-specified inclusion criteria or met at least 1 of the protocol-specified exclusion criteria
 
• Participant did not complete the protocol-defined vaccination schedule
 
• Participant received a study intervention other than the one that he/she was randomized to receive
 
• Preparation and/or administration of study intervention was not done as per-protocol
 
• Participant did not receive study intervention in the proper time window
 
• Participant received an authorized/approved COVID-19 vaccine prior to D36 visit
 
• Participant with a positive test result in the ELISA and/or neutralization test at baseline
 
 
Additional conditions for exclusion may be identified during the review of protocol deviations; such conditions will be documented in the Statistical Analysis Plan (SAP).

Per-Protocol Analysis Set for Immunogenicity (PPAS-IAS)	Subset of PPAS excluding participants who provided all post-dose serology samples outside the proper time window or no post-dose serology sample was drawn.
Per-Protocol Analysis Set for AIT (PPAS-AIT)	Subset of PPAS excluding participants who provided all post-dose AIT samples outside the proper time window or no post-dose AIT sample was drawn.

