### 9.4.3.2 Efficacy

Virologically-confirmed COVID-19-like illness is defined by the occurrence of a COVID-19 illness as described in [Section 8.2.2.1](#), associated with a positive NAAT for SARS-CoV-2 in a respiratory sample.

Serologically-confirmed SARS-CoV-2 infection is defined as a change from negative to positive (see [Section 8.2.2.1](#)) in the non-S immunoassay from any post-baseline sampling time-point compared to the baseline value, as measured in a SARS-CoV-2 Nucleoprotein specific antibody detection immunoassay.

Correlates of risk/protection analysis will be performed based on antibody responses to SARS-CoV-2 as evaluated using virus neutralization or binding antibody (ELISA), considering cases of virologically-confirmed COVID-19-like illness and/or serologically-confirmed SARS-CoV-2 infection as defined above. Detailed statistical methods will be described in the SAP.

Efficacy analyses will be performed on FAS and PPAS-IAS, unless otherwise specified.

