4.4.4 Efficacy

The efficacy endpoints are the virologically-confirmed COVID-19-like illness and serologic SARS-CoV-2 infection.

Virologically-confirmed COVID-19-like illness

Virologically-confirmed COVID-19-like illness is defined as a positive result for SARS-CoV-2 by Nucleic Acid Amplification Test (NAAT) on a respiratory sample in association with a COVID-19-like illness, which is defined in the protocol Section 8.2.2.1.

Serologically-confirmed SARS-CoV-2 infection

Serologically-confirmed SARS-CoV-2 infection is defined as a positive result in serum for the presence of antibodies specific to the nucleoprotein of SARS-CoV-2 detected by electrochemiluminescence immunoassay (ECLIA).

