5.1 Statistical Methods

Safety, immunogenicity, and efficacy analysis will be undertaken including those data collected before the date of receiving an authorized/approved COVID-19 vaccine. Those data collected on or after receiving an authorized/approved COVID-19 vaccine will be listed separately.

For those participants who did not receive an authorized/approved COVID-19 vaccine outside the study, immunogenicity data collected until the last scheduled/unscheduled study visit will be used for analysis. Rules about how to handle unscheduled visit are detailed in Table 5.2. Safety data collected until the last phone contact will be used for analysis if participants did not receive an authorized/approved COVID-19 vaccine outside the study

Safety analyses will be conducted based on two populations: *i*) participants in the Full Enrollment Cohort (Cohort 1 and 2) only, and *ii*) all participants in the Full Enrollment Cohort and Sentinel Cohort, if necessary. Immunogenicity analyses and efficacy analyses will be conducted based on the combined population (Full Enrollment Cohort + Sentinel Cohort) only, in which the same

dose-level group in Sentinel Cohort and Full Enrollment Cohort will be pooled. Subgroup analyses will be performed by age-group.

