5.2.4 Other Analysis Sets

Enrolled participants

All participants with a dose-level group that has been allocated by interactive response system (IRT).

Randomized participants

A randomized participant is a participant for whom a randomized group has been allocated by IRT.

Participants with data in CRF

Participants with data in CRF are participants for whom data were recorded at a visit (except screening).

Modified FAS (mFAS)

Subset of FAS that excludes participants with positive pseudovirus neutralization test results against SARS-CoV-2 D614G variant at baseline (D01).

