5.2.5 Populations Used in Analyses

Participants' disposition, demographics, baseline characteristics and exposure will be summarized by planned intervention group for all screened participants or Enrolled participants.

The primary safety analysis will be performed on the SafAS, SafAS1, and SafAS2 by injection group according to the vaccine received.

The primary immunogenicity analyses, the secondary immunogenicity analyses, and the exploratory immunogenicity analyses will be performed on the mFAS by injection group as actually received. This is due to a high rate of protocol deviations and dosing errors found in the preliminary analysis for sentinel cohort.

The secondary efficacy analysis will also be performed on the mFAS by injection group as actually received.

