5.7 Changes in the Conduct of the Trial or Planned Analyses

The content of the current SAP is based on protocol v3.0 and the following modifications.

When conducting the planned preliminary interim analysis, as the sensitivity of the rapid diagnostic test (RDT), used to assess seropositivity at screening, was low, an ad hoc analysis set "mFAS" was defined as a subset of the FAS that excludes participants with positive pseudovirus neutralization test results against SARS-CoV-2 D614G variant at baseline. In addition, due to 8 participants in the Sentinel Cohort with dosing errors related protocol deviations, immunogenicity analyses were performed using "mFAS" according to the study intervention participants actually received. The "mFAS" by injection group will also be used in the final analysis.

After the planned preliminary interim of the Sentinel Cohort participants, a decision to discontinue the development of the mRNA COVID-19 vaccine was made. On September 27, 2021, all Investigators were informed to terminate further vaccinations and enrollment. All

enrolled participants were to be unblinded to allow them to make their decision to receive an authorized COVID-19 vaccine. All clinical sites were to contact participants to inform them of the discontinuation of further study vaccinations, told what intervention they received and invited to come in for an unscheduled visit for counseling to answer any questions about the study, to discuss available options for receipt of an approved /authorized COVID vaccination, and were requested to provide unscheduled blood draw for serological assessment (UBXX). Participants were informed that additional D22 or D36 blood draws for serological assessment would be appreciated but are not mandatory. No protocol defined schedule visits or blood draws at timepoints later than D36 were required. Monitoring for SAEs, AESIs, medically attended AEs, and pregnancy and collection of influenza and COVID-19 vaccines were continued with safety calls. On March 15, 2022, after concurrence from regulatory authorities, Investigators were notified of the decision to end the study at the 6-month safety follow-up instead of 12-month follow-up.

As the further development of the mRNA COVID-19 vaccine was terminated and as mentioned above in [Section 5.4](#), interim analyses initially planned in the protocol will not be performed. The final analysis will be conducted in an unblinded manner.

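### SAP 4.4.4 omits the negative-to-positive condition for serologically-confirmed infection, so a participant already nucleoprotein-positive at D01 would count as an on-study case

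*SAP*

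**What the plan says.** Three places define serologically-confirmed SARS-CoV-2 infection.

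- Protocol 8.2.2.1: "Defined as a positive result in serum for the presence of antibodies specific to the nucleoprotein of SARS-CoV-2", by ECLIA. There is no baseline or timing condition.
- Protocol 9.4.3.2: "Serologically-confirmed SARS-CoV-2 infection is defined as a change from negative to positive", citing 8.2.2.1 and requiring a post-baseline sample set against the baseline value.
- SAP 4.4.4: "Serologically-confirmed SARS-CoV-2 infection is defined as a positive result in serum for the presence of antibodies specific to the nucleoprotein of SARS-CoV-2". This is the 8.2.2.1 rule alone. SAP 4.2 likewise sends the reader to protocol 8.2.2 for secondary efficacy and does not mention 9.4.3.2.

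On the population, SAP 5.2.5 says: "The secondary efficacy analysis will also be performed on the mFAS by injection group as actually received". SAP 5.2.4 defines the mFAS as the FAS without participants whose pseudovirus neutralization test against D614G was positive at D01. It has no exclusion on N antibody. Protocol 9.4.3.2 had planned efficacy on the FAS and the PPAS-IAS.

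SAP 1 says in general that Section 4 was modified for endpoint derivation. Neither that statement nor the list of changes in SAP 5.7 names this endpoint.

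**The concern.** Secondary efficacy objective 1 is to describe how often infection occurs in the study. A definition that accepts any N-positive serum also accepts the pre-vaccination sample, so an infection that came before the first injection can enter the count.

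The plan leaves room for this. Protocol Table 8.1 schedules the N immunoassay on the D01 sample, so a baseline positive would be recorded. SAP 5.7 explains that the mFAS was created "as the sensitivity of the rapid diagnostic test (RDT), used to assess seropositivity at screening, was low", so screening cannot be relied on to keep previously infected people out. The mFAS then removes only those whose earlier infection shows as a D01 neutralization titre at or above the LLOQ. Someone N-positive but below that limit stays in.

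Visits after D36 were no longer required once vaccination stopped (SAP 1). True late seroconversions may therefore be missed, while baseline positives would all be counted.

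**Working it through.** **Step 1. Apply both rules to the four possible N patterns.**

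| D01 N | Post-baseline N | SAP 4.4.4 | Protocol 9.4.3.2 |
|---|---|---|---|
| negative | negative | no case | no case |
| negative | positive | case | case |
| positive | positive | case | no case |
| positive | negative | case | no case |

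The rules agree for everyone N-negative at D01 and disagree for everyone N-positive at D01.

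**Step 2. Look for another safeguard.** The protocol's PPAS excluded a "Participant with a positive test result in the ELISA and/or neutralization test at baseline", but that ELISA measures anti-spike IgG (protocol 8.2.1.2), while N is measured by ECLIA (8.2.2.3). The protocol's FAS had no baseline serology exclusion, and the mFAS excludes on neutralization only. No analysis set in either document screens on N, so the 9.4.3.2 condition was the only element that did so. No other SAP section restores it.

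**Step 3. Effect of one false case in a group with no true case.** The documents give no figure to reproduce. Planned sizes are from protocol Tables 4.2 and 4.3. For the pooling, SAP 5.1 says: "efficacy analyses will be conducted based on the combined population (Full Enrollment Cohort + Sentinel Cohort) only", by dose level; SAP 5.1.1.2 and 5.1.1.4 join the Sentinel Cohort to Cohort 2; and SAP 5.2.5 analyses by injection group. I therefore keep Cohort 1 separate.

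- Two injections, Sentinel not expanded: 44 + 10 = 54
- Two injections, Sentinel expanded: 44 + 25 = 69 (low dose: 44 + 5 + 20, expansion already exercised per protocol 6.3.1)
- One injection, vaccine: 44
- Placebo, per schedule: 22

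The intervals are 95% Clopper-Pearson, as in SAP Section 5. For x = 0 the upper limit is 1 − 0.025^(1/n). For x = 1 the lower limit is 1 − 0.975^(1/n), and the upper limit is the 0.975 quantile of Beta(2, n − 1).

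| n | 0/n | 1/n |
|---|---|---|
| 54 | 0% (0 to 6.60) | 1.85% (0.05 to 9.89) |
| 69 | 0% (0 to 5.21) | 1.45% (0.04 to 7.81) |
| 44 | 0% (0 to 8.04) | 2.27% (0.06 to 12.02) |
| 22 | 0% (0 to 15.44) | 4.55% (0.12 to 22.84) |

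**Step 4. How many false cases?** This depends on q, the share of the mFAS that is N-positive but neutralization-negative at D01. The documents do not give q. For illustration only, the expected count is n × q and the chance of at least one is 1 − (1 − q)^n.

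| Assumed q | n = 100: expected (chance of at least one) | n = 333: expected (chance of at least one) |
|---|---|---|
| 0.5% | 0.5 (0.39) | 1.7 (0.81) |
| 1% | 1.0 (0.63) | 3.3 (0.97) |
| 2% | 2.0 (0.87) | 6.7 (1.00) |

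The 333 is the planned total. Enrollment stopped early and the mFAS removes some participants, so n = 100 is shown as a smaller alternative.

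**The case against.** The strongest reply is that the protocol does not contradict itself. Because 9.4.3.2 cites 8.2.2.1 inside its own definition, 8.2.2.1 can be read as saying what a positive result is and 9.4.3.2 as saying what the endpoint is. That reading is reasonable, but it does not rescue the SAP, which carries over the assay rule and leaves out the endpoint rule.

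A related reply is that SAP 5.7 bases the SAP on protocol v3.0 plus listed modifications and lists none for this endpoint, so 9.4.3.2 still governs. That makes the intention arguable. However, SAP 4.4.4 gives a complete definition in the section on calculation methods, and a programmer would follow it. The separate tables, listings and figures document might carry the condition, but it is not among the documents available here.

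On population, the mFAS is stricter than the protocol's FAS, and the PPAS never excluded on N. Both points are correct. The gap therefore lies in the endpoint definition and not in the choice of the mFAS.

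On size, SAP 5.1 read literally could pool both schedules within a dose: 44 + 44 + 10 = 98, where one false case moves 0% (0 to 3.7) to 1.0% (0.03 to 5.6). The effect is then smaller but in the same direction.

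Finally, no efficacy hypothesis is tested, and vaccine efficacy and correlates of risk are dropped (SAP 5.1.2.3, 5.1.2.4). This limits the consequences and stands in full.

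**Conclusion.** The concern holds. SAP 4.4.4 as written counts any mFAS participant who is N-positive at D01 as a serologically-confirmed infection, whatever the later results. Protocol 9.4.3.2 never counts such a participant.

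The effect falls on the number and percentage of cases with its 95% CI. One false case adds 1.4 to 4.5 percentage points to a group at planned sizes, under the by-schedule pooling above. The number of such participants is unknown and may be zero, and actual groups may be smaller than planned.

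The summary in SAP 5.1.3 of the last titre and concentration before infection is probably little affected. A participant N-positive at D01 has no pre-infection sample, and with no imputation (SAP 5.3.5) would most naturally drop out, although the SAP does not say so.

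This assessment assumes that the harm analysis in SAP 5.1.1.2, whose COVID-19 case is not defined there, does not use the serological endpoint.

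**What to change.** In SAP 4.4.4, define the endpoint as N-ECLIA negative at D01 and positive at any post-baseline sample. List participants who are N-positive at D01 separately. Do not count them as on-study cases, and leave them out of the SAP 5.1.3 summary of titres before infection. State in protocol 8.2.2.1 and 9.4.3.2 which text is the assay rule and which the endpoint, or declare the chosen definition in SAP 5.7.

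Two optional additions, which neither document sets for this endpoint:

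- List separately participants with no D01 N result and a later positive, since some may be true cases.
- Also report the percentage among participants who are N-negative at D01 and have a post-baseline N result.

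The cost is a few lines of SAP text and one derivation from D01 results already planned. The mFAS does not change. The only downside is a possibly lower count of infections.

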4.4.5 Derived Other Variables

4.4.5.1 Age for Demographics

The age of a participant in years in the study is the calendar age in years at the time of inclusion and will be analyzed as collected in CRF.

Age group

The calendar age will be used for age sub-groups definition. The age group of a participant in the study will be based on the calendar age as follows:

“18 to 49 years” means from the day of the 18th birthday to the day before the 50th birthday.

“Over 50 years” means from the day of the 50th birthday onwards, with no upper age limit.

If only year of birth is collected, use the calculated age in years to generate age group.

4.4.5.2 Duration of the Study

The duration of the study is computed in days as follows:

- Maximum (date of last visit, date of termination, date of last contact) – minimum (date of V01) +1

4.4.5.3 Participant Duration

The duration of a participant participation in the study is computed as follows:

Maximum (Visit dates, Termination date, contact dates) – V01 date + 1

5 Statistical Methods and Determination of Sample Size

The statistical analyses will be performed under the responsibility of the Sponsor’s Biostatistics platform using SAS® Version 9.4 or later.

The results of the statistical analysis will be available in the final clinical study report (CSR).

For descriptive purposes, the following statistics will be presented as shown in [Table 5.1](#).

Table 5.1: Descriptive statistics produced

Baseline characteristics and follow-up description	Categorical data	Number of participants. Percentage of participants and 95% CI.
	Continuous data	Mean, standard deviation, quartiles, minimum, and maximum.
Clinical safety results	Categorical data	Solicited: Number and percentage (95% confidence intervals [CIs]) of participants. Unsolicited: Number and percentage (95% CIs) of participants, and number of events.
Immunogenicity results	Categorical data (seroconversion, 2 fold-rise, 4 fold-rise)	Number and percentage (95% CIs) of participants.
	Continuous data (titer / data)	Anti-Log ₁₀ (work on Log ₁₀ distribution, and anti-Log ₁₀ applied): Geometric mean, 95% CI of the geometric mean, quartiles, minimum, and maximum. Graphical representation by Reverse Cumulative Distribution Curve (RCDC).
Efficacy results	Categorical data	Number and percentage (95% CIs) of participants.

The CI for the single proportion will be calculated using the exact binomial method (Clopper-Pearson method, quoted by Newcombe (4), ie, using the inverse of the beta integral with SAS®).

For immunogenicity results, assuming that Log₁₀ transformation of the titers / data follows a normal distribution, at first, the mean and the 95% CI will be calculated on Log₁₀ (titers / data) using the usual calculation for normal distribution (using Student's t distribution with n-1 degree of freedom), then antilog transformations will be applied to the results of calculations, in order to provide geometric means (GMs) and their 95% CI.

5.1 Statistical Methods

Safety, immunogenicity, and efficacy analysis will be undertaken including those data collected before the date of receiving an authorized/approved COVID-19 vaccine. Those data collected on or after receiving an authorized/approved COVID-19 vaccine will be listed separately.

For those participants who did not receive an authorized/approved COVID-19 vaccine outside the study, immunogenicity data collected until the last scheduled/unscheduled study visit will be used for analysis. Rules about how to handle unscheduled visit are detailed in Table 5.2. Safety data collected until the last phone contact will be used for analysis if participants did not receive an authorized/approved COVID-19 vaccine outside the study

Safety analyses will be conducted based on two populations: *i*) participants in the Full Enrollment Cohort (Cohort 1 and 2) only, and *ii*) all participants in the Full Enrollment Cohort and Sentinel Cohort, if necessary. Immunogenicity analyses and efficacy analyses will be conducted based on the combined population (Full Enrollment Cohort + Sentinel Cohort) only, in which the same

dose-level group in Sentinel Cohort and Full Enrollment Cohort will be pooled. Subgroup analyses will be performed by age-group.

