5.2.3 Per-Protocol Analysis Set

Subset of the FAS. Participants presenting with at least one of the following conditions will be excluded from the PPAS:

- Participant did not meet all protocol-specified inclusion criteria or met at least one of the protocol-specified exclusion criteria
- Participant did not complete the protocol-defined vaccination schedule
- Participant received a study intervention other than the one that he / she was randomized to receive
- Preparation and / or administration of study intervention was not done as per-protocol
- Participant did not receive study intervention in the proper time window as defined in the protocol visits.
- Participant receives an authorized/approved COVID-19 vaccine prior to D22 (Cohort 1) or D36 (Sentinel Cohort and Cohort 2).
- Participant with positive test results (\geq LLOQ) in the pseudovirus neutralization test* at baseline.

*Only SARS-CoV-2 D614G variant will be considered.

The above conditions leading to exclusion from the PPAS may be detailed and completed if necessary, following the data review. In any case, if PPAS definition is modified, the PPAS definition will be finalized before the database lock and documented in an SAP update.

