In addition, the following analyses planned at the time of the protocol or previous version of SAPs will not be performed:

- Between groups ratios of neutralizing Ab GMTs and between group seroconversion rates differences
- Between groups ratios of anti-S antibody concentrations and between group seroconversion rates differences
- Correlated of risk and of vaccine efficacy
- Complementary analysis and sensitive analysis on immunogenicity data and safety data
- Safety and immunogenicity analyses by aggregated groups

Detailed analyses can be found in the SAP document of Tables, Listings and Figures.

6 References List

4. Newcombe RG. Two-sided confidence intervals for the single proportion: comparison of seven methods. *Stat Med.* 1998;17(8):857-72.
5. Agresti, Alan (2002). *Categorical Data Analysis (Second ed.)*. Wiley. ISBN 0-471-36093-7.

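### SAP 5.1 stops immunogenicity data at outside COVID-19 vaccination but not at documented SARS-CoV-2 infection, and the mFAS defines naive status by pseudovirus alone without SAP 5.7 naming the lost ELISA criterion (minor)

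*SAP*

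**What the plan says.** **Data cut.** SAP 5.1 analyzes data collected before an outside COVID-19 vaccine and says of the rest: "Those data collected on or after receiving an authorized/approved COVID-19 vaccine will be listed separately". For participants with no outside vaccine, "immunogenicity data collected until the last scheduled/unscheduled study visit will be used for analysis". SAP 4.4.2, 5.2 and 5.3.2 contain no rule on samples drawn after infection. SAP 5.1.3 describes the last titer before infection among cases, which is exploratory and leaves the main tables unchanged.

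**Analysis set.** SAP 5.2.5 puts the primary, secondary and "exploratory immunogenicity analyses will be performed on the mFAS by injection group as actually received". SAP 5.2.4 defines that set as "Subset of FAS that excludes participants with positive pseudovirus neutralization test results against SARS-CoV-2 D614G variant at baseline (D01").

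**Baseline criterion.** The PPAS in Protocol 9.3 excludes: "Participant with a positive test result in the ELISA and/or neutralization test at baseline". The SAP's own PPAS (5.2.3) excludes only positives "in the pseudovirus neutralization test* at baseline", limited to D614G.

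**Disclosure.** SAP 5.7 introduces the mFAS "as the sensitivity of the rapid diagnostic test (RDT), used to assess seropositivity at screening, was low". It then says that "the following analyses planned at the time of the protocol or previous version of SAPs will not be performed" and gives a list, which includes sensitivity analyses. Nowhere does it mention ELISA.

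**The concern.** SAP 5.1 accepts that antibody from a non-study source should not be counted as group response, but applies this to outside vaccination and not to infection. Infection can raise GMTs, fold-rise and seroconversion, and the effect is easiest to see where titers would otherwise sit at LLOQ/2, in the placebo groups.

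The baseline matter is related. Protocol 4.2 aims the trial at a naive population and expects prior exposure to affect immunogenicity measures. The mFAS was created because the screening test missed seropositive people. It removes those who neutralize D614G, but not those positive only by ELISA or nucleoprotein.

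The between-group GMT ratios and seroconversion differences are cancelled (SAP 5.1.1.4 and 5.7). What is at stake is therefore how each group is described in the final report.

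**Working it through.** The plan gives no figure on this point, so there is none to reproduce. The check compares texts and then illustrates size on assumed inputs.

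**Step 1: which SAP choices add exposure.**
- *Set.* Protocol 9.4.2.1 uses the PPAS-IAS. Under DCI05 (Protocol 7.1.2), a NAAT-confirmed symptomatic case between V01 and V03 gets no second dose. That participant leaves the PPAS because the schedule is incomplete. The mFAS has no such condition and keeps the participant.
- *Visit mapping.* SAP 5.1 sends unscheduled samples to Table 5.2 without restricting this to late visits. D36 is a primary timepoint.

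| Schedule | Protocol window for D36 | Table 5.2, unscheduled samples |
|---|---|---|
| 1 injection | V01+35 to V01+42 (8 days) | V01+32 to V01+66 (35 days) |
| 2 injections | V03+14 to V03+21 (8 days) | V03+13 to V03+55 (43 days) |

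A sample labeled D36 can thus be drawn up to 66 − 42 = 24 days, or 55 − 21 = 34 days, after the protocol window closes.

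**Step 2: baseline status.** The protocol PPAS uses ELISA and/or neutralization; the mFAS uses D614G pseudovirus only. Protocol Table 8.1 schedules the nucleoprotein assay on BL0001 (D01), and Protocol 9.4.3.2 uses the baseline result as the reference for serological infection. SAP 4.4.4 counts any nucleoprotein-positive serum as infection. A participant nucleoprotein-positive but pseudovirus-negative at D01 would therefore meet that infection definition and stay in the mFAS.

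**Step 3: size of one later infection.** Planned sizes come from Protocol Tables 4.2 and 4.3: placebo 22 per schedule (10 and 12 by age), vaccine 44 (20 and 24 by age). Pooled with Sentinel (SAP 5.1.1.4), two-injection groups are 44 + 10 = 54 or 44 + 25 = 69. Their 18-49 strata are 20 + 10 = 30 or 20 + 25 = 45. Assumed: one infected participant rises F = 32 to 128-fold over LLOQ/2, and the other placebo recipients stay at LLOQ/2.

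Placebo GMT factor = F^(1/n); seroconversion limits are Clopper-Pearson:

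| n | F=32 | F=64 | F=128 | 0 of n (95% CI) | 1 of n (95% CI) |
|---|---|---|---|---|---|
| 22 | 1.171 | 1.208 | 1.247 | 0% (0-15.4) | 4.5% (0.1-22.8) |
| 12 | 1.335 | 1.414 | 1.498 | 0% (0-26.5) | 8.3% (0.2-38.5) |
| 10 | 1.414 | 1.516 | 1.625 | 0% (0-30.8) | 10% (0.3-44.5) |

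Vaccine group already at an assumed 16-fold rise, factor = (F/16)^(1/n), F = 32 to 128:
- n=44: 1.016 to 1.048
- n=54: 1.013 to 1.039
- n=69: 1.010 to 1.031
- n=20: 1.035 to 1.110
- n=24: 1.029 to 1.091
- n=30: 1.023 to 1.072
- n=45: 1.016 to 1.047

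**Step 4: one primed participant missed at baseline.** Assume a pseudovirus-negative vaccinee whose post-dose titer is B = 4 or 16 times the arm's. The neutralization GMT factor B^(1/44) is 1.032 or 1.065. If that person's baseline ELISA is K = 8 times LLOQ/2, the ELISA fold-rise factor is (B/K)^(1/44): 0.954 with no extra response (B=1) and 1.016 with B=16. The effect on ELISA fold-rise can go either way.

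**Step 5: chance of at least one infection in a placebo group of 22.** 1 − (1 − a)^22 gives 19.8%, 48.8%, 67.6% and 90.2% at assumed cumulative attack rates a of 1%, 3%, 5% and 10%.

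**The case against.** A reader might infer that the SAP departs from the protocol by not cutting at infection. It does not: the protocol has no such rule, and its PPAS-IAS lost infected participants only incidentally. The primary objective describes each group's neutralizing profile with no infection-free condition, and the Protocol 4.2 statement on prior exposure concerns enrollment. Antibody from natural infection in placebo recipients can fairly be called background.

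A reader might also infer that the change of naive definition was hidden. SAP 5.7 openly gives the pseudovirus-only mFAS and its reasons. The list that follows covers analyses not performed, not population criteria. SAP 5.2.5 assigns no analysis to the PPAS, so the altered PPAS bullet changes no planned result. What is missing is an explanation of the ELISA change.

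The GMT effect is modest. The worst placebo case, 1.625 × 0.5 LLOQ = 0.81 LLOQ, is still below quantification. Quartiles, extremes and reverse cumulative curves would show an outlying titer. The separate tables, listings and figures document, not available here, may already flag infections.

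Censoring at infection also conditions on a post-vaccination outcome and may remove low responders. This argues against making it the main analysis.

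Most of this stands and sets the weight of the point. It does not remove it. A GMT below LLOQ does not stop one infection counting as a seroconversion. An outlying titer on a curve does not show its cause. With sensitivity analyses cancelled, nothing in the SAP separates infection from vaccine response in the main summaries.

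**Conclusion.** The point holds as a minor one. Followed as written, the plan counts infection-induced antibody as group response in the only set used for immunogenicity, and two SAP choices enlarge that exposure. The naive definition is narrower than the protocol's, and the ELISA change is neither named nor justified.

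The size is unknown. All rises and attack rates above are assumptions and the arm sizes are planned. Enrollment stopped early (SAP 1), so actual groups may be smaller and one infection would weigh more. The effect is probably small in vaccine groups and matters mainly for placebo seroconversion and small age strata.

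The documents do not support a claim that the reported vaccine GMTs are materially inflated. Nor do they show that the mFAS contains many previously infected people: they do not say how many participants were positive only by ELISA or nucleoprotein.

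**What to change.** 1. Keep the planned mFAS summaries. Add one parallel table of GMT, fold-rise and seroconversion that leaves out participants nucleoprotein-positive at D01, and samples drawn on or after the first positive NAAT or the first post-D01 nucleoprotein-positive sample (where tested). List the omitted samples. Label the table supportive and show it beside the uncensored results.
2. In SAP 5.7, state and justify the removal of the baseline ELISA criterion, or restore it with a stated positivity cutoff. Protocol 9.3 gives no ELISA cutoff, and SAP 5.2.3 defines positivity (at or above LLOQ) only for the pseudovirus test.

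**Cost.** One table, one listing and a few sentences. NAAT results are collected and nucleoprotein testing is scheduled on BL0001 to BL0006. SAP 5.1.3 already needs to know when infection occurred. The supportive table has slightly smaller n and may selectively lose low responders. Nucleoprotein results only bracket the infection date, and may be missing for unscheduled draws, for which the documents do not specify that assay. This SAP version serves an unblinded final analysis, so the rule should be written down before database lock.
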